**Table 3: Post-Baseline Analysis Visit and Analysis Window**

Post-Baseline Analysis Visit (Target Assessment Date)	Visit Window	Analysis Window
Week 1 (Day 8)	[7, 9]	[2, 18]
Week 4 (Day 29)	[26, 32]	[19, 43]
Week 8 (Day 57)	[54, 60]	[44, 71]
Week 12 (Day 85)	[81, 89]	[72, 99]
Week 16 (Day 113)	[109, 117]	[100, 127]
Week 20 (Day 141)	[137, 145]	[128, 155]
Week 24 (Day 169)	[164, 174]	[156, 183]
Week 28 (Day 197)	[192, 202]	[184, 211]
Week 32 (Day 225)	[220, 230]	[212, 253]

For analyses involving post-baseline visits, if there are two or more measurements that fall into the same analysis window of a post-baseline visit, then the measurement at visit with any injection will be selected. If there is no visit with any injection, then the measurement closest to the target assessment day will be selected for that visit. In the case that two measurements are equidistant to the target assessment day, i.e., one is before and one is after the target assessment day, the later one will be selected for that visit.

#### 4.1.6. Days on Treatment

*Days on treatment* measures the duration of exposure to a study medication received during the study. For this study, the days on treatment is defined as:

- Days on treatment = (date of last dose – date of first dose) + 1

## 4.2. Efficacy-Related Definitions

### 4.2.1. Study Eye and Fellow Eye

The *study eye* of a randomized, treated subject is the eye that was injected with study medication at baseline (Day 1). For subjects who were randomized but not treated, the study eye is the eye determined to be injected by the Clinical Investigator at baseline (Day 1). The Clinical Investigator selected “OD” or “OS” for “Study Eye” on the Primary Diagnosis eCRF.

*Fellow eye* is the non-study eye.

### 4.2.2. Baseline Score

For any measure, the *baseline score* is the last observed measurement prior to the initial injection of study medication at the baseline visit.

### 4.2.3. Change and Percent Change from Baseline

The change and the percent change from baseline in a measure at a post-baseline visit will be defined as:

- Change = score at the post-baseline visit – baseline score.
- Percent change from baseline =  $100 \times \text{change} / (\text{baseline score})$ .

### 4.2.4. Efficacy Measures

Table 4 lists all the efficacy measures to be evaluated for this study.

**Table 4: Efficacy Measures (Continued)**

Efficacy Measures	Note
Total lesion area	Total lesion area is defined as the entire complex of lesion components (mm  ), which is the sum of total CNV area and the areas of each of the non-CNV lesion components. Total lesion area will be determined by FA.
Total area of choroidal neovascularization (CNV)	The total area of CNV measures the total area of new blood vessels that originate from the choroid and extend through Bruch's membrane into the subretinal pigment epithelium (sub-RPE). The total area of CNV will be measured in mm  . 'Ungradable' may be selected when the FA image is unable to measure for any reason.
Greatest linear dimension of the total lesion area (GLD)	GLD of the total lesion area is measured from the total lesion area (mm) determined by FA.

### 4.3. Safety-Related Definitions

#### 4.3.1. Adverse Event

An AE is any untoward medical occurrence in a subject administered a pharmaceutical product and which does not necessarily have a causal relationship with the study drug(s).

An on-study AE can occur at any time after the date of informed consent through the last study visit. An AE will be considered as treatment-emergent if the AE onset occurs on or after the analysis period start date and prior to or on the on-treatment analysis period end date as defined in [Section 4.1.4](#). Treatment-emergent AEs are a subset of on-study AEs. Both on-study and treatment-emergent AEs are to be recorded, but only treatment-emergent AEs will be tabulated.

Each AE will be classified into a system organ class (SOC) and coded to a preferred term (PT) using Medical Dictionary for Regulatory Activities (MedDRA), version 20.0 published in 2017.

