12. ASSESSMENT OF SAFETY

12.1. Adverse Events

12.1.1. Definition of Adverse Events

An AE is any untoward medical occurrence in a subject administered a pharmaceutical product and which does not necessarily have a causal relationship with the study drug(s). An AE, therefore, can be an unintended sign (including an abnormal laboratory finding), symptom, or disease that has clinical significance and is temporally associated with the use of a medicinal (investigational) product, whether or not related to the medicinal (investigational) product.

In clinical studies, an undesirable medical condition occurring at any time, including baseline or pre-treatment period, may be recorded as an AE even if no study drug has been administered.

Any significant adverse change in a subject's condition from baseline, regardless of causality, is to be considered an AE, unless the change is determined to be a continuation of a pre-existing condition that is documented in the subject's medical history. However, a clinically significant worsening in severity, intensity, or frequency of a pre-existing condition may indicate an AE. In addition, all conditions that lead to hospitalizations, defined as an overnight hospital stay, are considered as AEs. This includes planned elective surgeries.

Lack of efficacy of the study drug(s) for the condition being investigated is not considered an AE unless a clinically significant change is assessed by the Clinical Investigator. An elective surgical procedure scheduled or planned prior to study entry is not considered an AE if an overnight hospital stay is not required, and the underlying diagnosis for which surgery is to be performed should be captured in the medical history as a pre-existing condition. The surgical procedure should also include the term "elective" in all reports.

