- For intermittent events (e.g., intermittent headache), the event onset date should be recorded as the date the subject first started to experience the event and resolution date should reflect when the last occurrence resolved or stopped. Separate AEs for each event should not be recorded. For example, if a subject experienced headache on 14SEP2015 lasting for three hours, then subsequently experienced intermittent episodes of headache every day for approximately 3 hours until 21SEP2015, then the AE date of onset is 14SEP2015 and the resolution date is 21SEP2015.
- For intermittent events, record the maximum severity of the individual events. For example, if a subject complains of intermittent headaches for one week and the severity of each headache ranges from mild to moderate, then the severity would be moderate.
- For intermittent hospitalizations occurring for a primary AE (e.g., in a subject with multiple sclerosis, commonly known for its relapsing and remitting course, in some cases leading to multiple hospital confinements), the subsequent hospitalizations should be described in the narrative description of the case.
- If treatment was initiated, include the treatment and duration of the medication(s) in the eCRF.

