**Table 2: Analysis Periods**

Analysis Period	Analysis Period Start Date	Analysis Period End Date
On-treatment Period	The date of the first Lucentis® injection	The date of the Week 24 visit, or the Study Exit date, whichever came first
Follow-up Period	The date of the first day after Week 24 visit	The Study Exit date
Entire Study	Efficacy: the date of randomization; Safety: the date of the first Lucentis® injection	The Study Exit date

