### **9.1. Adverse Event**

Subjects with any AE(s), SAE(s), SAR(s), serious SAR(s) and ESI(s) will be tabulated for each actual treatment received. Besides the overall AE summary, subjects with any AE(s) will be tabulated by SOC and PT specified in MedDRA Version 20.0. Subjects with any AE(s) will also be tabulated by SOC, PT and maximum severity. A subject who experienced multiple AEs within a SOC or PT will be counted only once at the maximum severity for that SOC or PT. SAEs, SARs, and Serious SARs will be tabulated similarly.

Summaries for ocular AEs and non-ocular AEs will also be performed. Ocular AEs, ocular SAEs and ocular SARs will be summarized for study eyes and fellow eyes separately. Any ocular AE that occurred simultaneously to both eyes will be counted once for both the study eye and the fellow eye.

All AE tabulations will be performed on the Safety population for the On-treatment period, Follow-up period and entire study.

AEs, AEs leading to death, AEs leading to discontinuation, SAEs, and ESIs, if any, will be listed separately.

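### SAP 4.3.1 has no worsening clause, so a screening-onset AE that worsens after the first injection is left out of every AE table unless the site enters it as a new AE

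*SAP*

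**What the plan says.** SAP 4.3.1 sets the rule: "An AE will be considered as treatment-emergent if the AE onset occurs on or after the analysis period start date", with the end of the on-treatment period as the other limit. It adds that "only treatment-emergent AEs will be tabulated". Worsening is not mentioned.

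SAP Table 2 starts the On-treatment period at the first Lucentis injection. It starts the Entire Study period at one of two dates: "Efficacy: the date of randomization; Safety: the date of the first Lucentis® injection". The Follow-up period begins the day after the Week 24 visit. SAP 9.1 uses these three periods and no others: "All AE tabulations will be performed on the Safety population for the On-treatment period, Follow-up period and entire study".

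Protocol 12.1.1.2 requires AEs to be recorded from informed consent, including before treatment. For intermittent events it dates the record at the first occurrence and says: "Separate AEs for each event should not be recorded". On grading it says: "For intermittent events, record the maximum severity of the individual events". Protocol 12.1.1 says that "a clinically significant worsening in severity, intensity, or frequency of a pre-existing condition may indicate an AE".

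**The concern.** A definition of treatment-emergence normally covers two cases: events that start on treatment, and events that start earlier and worsen on treatment. SAP 4.3.1 covers only the first. Screening runs from Day -14 to Day -1 and includes fluorescein angiography, so some AEs can be expected to carry onset dates before Day 1.

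At stake are the tables that compare safety across arms. Safety against Lucentis alone is part of the primary objective. An on-treatment worsening that keeps a screening onset date adds nothing to incidence, maximum severity, SAE or suspected-reaction counts. The rule can remove such worsening from the AE tables but cannot add any.

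**Working it through.** The SAP states no figure on this point, so the check traces the rules and then works out the weight of one subject.

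**Step 1. Does any analysis period admit a screening-onset record?** On-treatment and Entire Study (safety) both begin on the date of the first Lucentis injection, and Follow-up begins later. A record dated before that day falls in none of them, so it enters no AE table under SAP 9.1. Because the start is a calendar date, an event that begins on Day 1 before the injection does count. The gap concerns records dated before the day of the first injection.

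**Step 2. How may a later worsening be recorded?** Take an AE with onset in screening that worsens after the first injection.

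| Case | Record under the protocol | Result under SAP 4.3.1 |
|---|---|---|
| (a) Intermittent event | One record, first onset date, maximum severity (12.1.1.2) | Not treatment-emergent; in no AE table |
| (b) Continuous event, existing record updated | One record, screening onset date | Not treatment-emergent; in no AE table |
| (c) Worsening entered as its own AE (12.1.1; Appendix D for physical-examination findings) | New record, onset at the worsening | Treatment-emergent if on or before the Week 24 visit; tabulated |

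In case (a), following both documents as written produces the omission. For a continuous event already recorded as an AE, neither document says whether (b) or (c) applies, so sites can handle like cases differently.

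**Step 3. Is the date of worsening available?** For intermittent events the protocol calls for the first onset date, the resolution date and the maximum severity. It does not call for the date on which severity changed. The AE record therefore cannot show whether the maximum was reached before or after the first injection.

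**Step 4. Weight of one subject.** This assumes that the Safety Population equals the arm sizes in SAP 3.3. One subject missing from a row lowers that row by 1/n:

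- Arm 1: 1/17 = 5.9 percentage points
- Arm 2: 1/31 = 3.2 percentage points
- Arm 3: 1/28 = 3.6 percentage points

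The expected number of such subjects cannot be calculated, because neither document gives a rate of screening-onset AEs or of their worsening.

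**The case against.** The strongest reply is that the protocol already handles this. Protocol 12.1.1 treats a significant adverse change from baseline as an AE, except where it is judged a continuation of a documented pre-existing condition. Baseline is the last pre-injection value. Appendix D says that worsening of abnormalities already noted on physical examination is assessed as an AE. A site that follows these passages can enter the worsening with its own onset date, and it is then tabulated. This stands. A reader might infer that every screening-onset AE that worsens is lost from the tables, and the documents do not support that. The reply does not reach intermittent events, where 12.1.1.2 forbids a separate record. It also does not settle continuous events already recorded as AEs, because the sentence on pre-existing conditions is only permissive.

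A second reply is that the intermittent-event rule is illustrated by a daily headache over about a week, so a clinically distinct later event need not be merged with an earlier one. That is fair, and it narrows the group. A recurring event that starts in screening and continues past Day 1 still falls squarely under the rule.

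Third, the information is not hidden. SAP 9.1 lists AEs, SAEs and ESIs, and SAEs need their own form within 24 hours. SAP 9.2, 9.3, 9.6 and 9.8 summarize worsening on slit-lamp, ophthalmoscopy, EKG and laboratory assessments whatever the AE onset date. In a descriptive study of about 76 subjects the listings can be read case by case. A reader might infer that such worsening appears only in a listing, and for these assessments that is wrong. Symptoms and diagnoses outside them do depend on the listing, which does not give incidence by arm.

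Finally, a reader might infer that the rule hides DE-122 toxicity in particular. The cut-off is the first Lucentis injection and applies in all three arms. Nothing in the documents shows that the omission would differ by arm.

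**Conclusion.** The definitional gap is real and its scope is limited. Omission from the AE tables is certain for an intermittent event that starts in screening and is recorded as the protocol requires. For a continuous event it depends on whether the site opens a new record. It does not occur when the worsening is entered as a new AE up to the Week 24 visit.

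The number affected is unknown, is probably small and may be zero, because the window is 1 to 14 days and no rate is given. The figures of 5.9, 3.2 and 3.6 points show how much one subject weighs in a row. They are not an estimate of the understatement, and they assume that the planned arm sizes hold in the Safety Population. The gap does not undermine the safety analysis as a whole, but it is a rule that can miscount on-treatment worsening and it is cheap to correct before unmasking.

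**What to change.** 1. In SAP 4.3.1, define treatment-emergent as onset on or after the first injection, or onset before it with worsening in severity, frequency or seriousness on or after it.
2. The SAP sentence is not enough alone, because the AE record holds no date of worsening. Before unmasking, review every AE with onset before the first injection that was ongoing or recurred on or after Day 1. Take the date of worsening from source records, which Protocol 20.2.1 requires to document the occurrence and status of AEs. Alternatively, have the eCRF guideline require a new record or a dated severity change in these cases, and state that this overrides the single-record rule for intermittent events.
3. Where the timing cannot be established, count the event as treatment-emergent.

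The cost is a short SAP edit, a masked review of what is likely to be a small number of records, and some return to source or a guideline note. A few more events may be counted, including some whose worsening in fact came before the first injection.

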12.1.1.2. Reporting Adverse Events

AEs, whether spontaneously reported by the subject or noted by authorized study personnel, will be recorded in the subject's medical record and on the appropriate AE eCRF. Each recorded AE will be described by its duration (i.e., start and end dates), frequency, severity, regulatory seriousness criteria if applicable, suspected relationship to the study drug(s), relation to injection procedure, location, actions taken and outcome.

AEs that occur after any subject has provided written informed consent, before treatment, during treatment, or until study exit visit, whether or not they are related to the study, must be recorded. To improve the quality and precision of acquired AE data, Clinical Investigators should observe the following guidelines:

- Whenever possible, use recognized medical terms when recording. Do not use colloquialisms and/or abbreviations.
- If known, record the diagnosis (i.e., disease or syndrome) rather than component signs and symptoms and /or laboratory or test findings (e.g., record congestive heart failure rather than dyspnea, rales, and cyanosis, and enlarged heart on chest x-ray). However, other events that are considered unrelated to an encountered syndrome or disease should be recorded as individual AEs (e.g., if congestive heart failure and severe headache are observed at the same time and are clinically unrelated, each event should be recorded as an individual AE).

If the diagnosis is not known, then record the leading component sign, symptom or test finding and describe the other clinically related findings in the narrative description of the case. A suspected diagnosis can be used and described as such

(e.g., record suspected or probable myocardial infarction); this has to be updated in the clinical database once the diagnosis is confirmed.

AEs occurring secondary to other events (e.g., sequelae) should be identified by the primary cause. A primary AE, if clearly identifiable, generally represents the most accurate clinical term. If a primary AE is recorded, events occurring secondary to the primary event should be described in the narrative description of the case. For example:

The subject developed orthostatic hypotension and subsequently fainted and fell to the floor wherein she experienced a head trauma and neck pain.

The primary AE in this example is orthostatic hypotension. The fall, head trauma and neck pain should be described in the narrative description of the case.

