16.7. Safety Analysis

All safety outcome measures will be summarized descriptively for the Safety Population. The safety outcome measures include adverse events (AEs), BCVA, slit-lamp biomicroscopy, indirect ophthalmoscopy, intraocular pressure (IOP), serum chemistry, hematology, urinalysis, vital signs, physical examination, fundus photography, fluorescein angiography, EKG and pregnancy.

AEs will be coded using the Medical Dictionary for Regulatory Activities (MedDRA).

Subjects with any AEs will be tabulated by system organ classification and preferred term specified in the MedDRA. Similarly, subjects with any ocular and non-ocular AEs and ESIs will be tabulated separately. AEs, ocular and non-ocular, as well as ESIs will also be summarized by relationship to treatment and maximum severity. In addition, SAEs and discontinuations due to AEs will be summarized.

Ocular safety outcome measures will be summarized using descriptive statistics.

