### 3. STUDY DESIGN

#### 3.1. General Study Design

This is a randomized, double masked and active controlled study assessing the safety and efficacy of repeated intravitreal injections of DE-122 (2.0 mg or 4.0 mg) in combination with Lucentis® compared to Lucentis® monotherapy in subjects with wet AMD. Seventy-six (76) subjects with wet AMD were randomly assigned to one of three treatment arms in two stages:

[figure not shown]
- Arm 1: Sham + Lucentis® 0.5 mg (N=17)
- Arm 2: DE-122, 2.0 mg + Lucentis® 0.5 mg (N=31)
- Arm 3: DE-122, 4.0 mg + Lucentis® 0.5 mg (N=28)

As shown in the Study Design Diagram ([Figure 1](#)), this study will consist of two stages. In Stage 1, the first 6 subjects will be randomized to either Arm 1 or Arm 2 in a 1:1 ratio. After all the 6 subjects have completed the Week 4 visit, the Safety Review Team will review the data to determine whether or not the safety and tolerability is acceptable. Subsequently in Stage 2, approximately 70 subjects will be randomized in a 1:2:2 ratios among the three arms.

Subjects will receive, in combination with Lucentis®, either 6 monthly intravitreal injections of DE-122 (2.0 mg), DE-122 (4.0 mg), or Sham in the study eye. The Primary Analysis is planned when all subjects complete the Week 24 visit. The Follow-up Analysis is planned at Week 32 to assess the number of anti-VEGF injections used for Rescue in addition to efficacy and safety data.

To be eligible, a subject must have been previously treated (i.e., At least 3 IVT injections of Anti-VEGF for treatment naïve eyes or eyes adequately maintained on continuous intravitreal anti-VEGF therapy). This condition was not required for subjects who enrolled before Protocol Amendment 06.

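### SAP 4.3.1 tabulates only adverse events with onset up to the Week 24 visit, but SAP 9.1 requires adverse event tables for the Follow-up period that starts the next day and for the entire study

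*SAP*

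**What the plan says.** **Definition.** SAP 4.3.1 calls an AE treatment-emergent if its onset is on or after the analysis period start and "prior to or on the on-treatment analysis period end date as defined in" Section 4.1.4. It then restricts the tables: "Both on-study and treatment-emergent AEs are to be recorded, but only treatment-emergent AEs will be tabulated".

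**Periods.** In SAP Table 2 the On-treatment period ends at "The date of the Week 24 visit, or the Study Exit date, whichever came first". The Follow-up period begins on "The date of the first day after Week 24 visit" and runs to Study Exit. For safety, the entire-study period runs from the first Lucentis injection to Study Exit.

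**Required tables.** SAP 9.1 states: "All AE tabulations will be performed on the Safety population for the On-treatment period, Follow-up period and entire study".

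**Purpose and data.** SAP 3.1 plans a Week 32 Follow-up Analysis of the number of rescue injections "in addition to efficacy and safety data". Protocol 12.1.1.2 requires recording of "AEs that occur after any subject has provided written informed consent, before treatment, during treatment, or until study exit visit". Protocol 16.7 sets no Week 24 limit: "Subjects with any AEs will be tabulated by system organ classification and preferred term specified in the MedDRA".

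**The concern.** Section 4.3.1 removes from all tables exactly the events that the Follow-up tables in 9.1 exist to show. Safety is part of the primary objective, and the Week 32 analysis is meant to report it. Under a literal reading of 4.3.1, its AE tables would show zero in every arm whatever had happened, and a reader could take that for an absence of events.

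What would be lost is the by-arm count, after Week 24, of AEs, serious AEs, suspected adverse reactions and events of special interest. Some of these have no other route into a summary table:

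- Protocol 12.1.3 names epistaxis and gingival bleeding as events of special interest, and no by-visit examination table would show them.
- Protocol Appendix D (23.4.2) has new physical-examination abnormalities at Study Exit assessed as AEs, and SAP section 9 plans no separate physical-examination summary.
- Under Protocol 7.5.2.12, a pressure rise that meets the reporting criteria after a Week 28 rescue injection is reported as an AE, but it would enter no AE table.

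There is a second, smaller problem. Table 2 anchors both periods to the Week 24 visit and does not say what happens when a subject misses that visit but stays in the study.

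**Working it through.** The plan gives no figure of its own here. The check compares the sets of onset days that each rule admits.

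**Inputs.** First Lucentis injection: Day 1. Week 24 visit: target Day 169, window 164 to 174. Week 32/Exit: target Day 225, window 220 to 230 (SAP Table 3). Planned subjects: 76.

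**Step 1: overlap at the target days.**
- Tabulated under 4.3.1: Days 1 to 169.
- Follow-up under Table 2: Days 170 to 225.
- Days in both: 0, so the Follow-up AE tables are empty by definition.
- Entire study (Days 1 to 225) restricted to 4.3.1: Days 1 to 169, which is the on-treatment set.

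**Step 2: size of the gap.** Days excluded = exit day − Week 24 visit day. Share = days excluded / exit day.

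| Week 24 visit | Exit | Days excluded | Share | Overlap with 4.3.1 |
|---|---|---|---|---|
| Day 169 | Day 225 | 225 − 169 = 56 | 56/225 = 24.9% | 0 |
| Day 174 | Day 220 | 220 − 174 = 46 | 46/220 = 20.9% | 0 |
| Day 164 | Day 230 | 230 − 164 = 66 | 66/230 = 28.7% | 0 |

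If all 76 subjects complete on the target days, this is 76 × 56 = 4,256 of 76 × 225 = 17,100 subject-days, the same 24.9%.

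**Step 3: can another reading remove the conflict?** The start of the window in 4.3.1 is worded generically and could be read period by period. The end is still explicitly the on-treatment one. A treatment-emergent AE in Follow-up would then need onset both after the Week 24 visit day and no later than it, which is impossible.

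**Step 4: a missed Week 24 visit.** Take two subjects, each with an AE starting on Day 197 and exit on Day 225.
- The first attended Week 24 on Day 169. On-treatment ended that day, 197 > 169, and the event is not tabulated.
- The second had no Week 24 visit. Only Study Exit remains as the end of On-treatment, 197 ≤ 225, and the event is tabulated as on-treatment. Follow-up has no start date for this subject.

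The same onset day is therefore counted or dropped according to attendance. Subjects who leave before Week 24 raise no conflict, because they have no follow-up time.

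**The case against.** The best answer is that 9.1 is the operative analysis section and is explicit. Table 2, SAP 3.1 and Protocol 16.7 all point the same way, and only one sentence in a definitions section points the other way. Its mixed wording, with a generic start and an on-treatment end, looks like a drafting slip. A programmer faced with a table that is empty by construction would probably raise a query. The study is descriptive and small, so listings can be read through.

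Much of this stands as an argument about likelihood. The empty table arises only if 4.3.1 is followed literally, and 9.1 does plan the missing summary. It does not remove the conflict. The SAP introduction says that the document gives detailed instructions for each analysis and that departures must be justified and documented in the study report. Following 9.1 breaks an explicit restriction, following 4.3.1 breaks 9.1, and no passage ranks them. A listing is also not a by-arm count.

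The missed-visit problem may be narrow. SAP Table 3 maps measurements on Days 156 to 183 to the Week 24 analysis visit, but the SAP does not say whether a visit in that range fixes the period boundary for AEs. The documents give no number of subjects affected.

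**Conclusion.** The two sections contradict each other and should be reconciled before the tables are produced. Under a literal reading of 4.3.1, and for subjects with a Week 24 visit, the Follow-up tables of AEs, serious AEs, suspected adverse reactions and events of special interest are empty, and the entire-study tables repeat the on-treatment ones. The excluded span is 56 of 225 days (24.9%), ranging from 20.9% to 28.7% if both visits fall within their windows.

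The share of events affected is unknown. The documents give no AE rate by period, and all six scheduled injection sessions, from Day 1 to Week 20, fall inside the tabulated window.

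The consequence is limited. The Week 24 primary analysis does not change, and events starting on the Week 24 visit day are counted. Later AEs, serious AEs and events of special interest are still recorded and listed. The slit-lamp, ophthalmoscopy, intraocular pressure, vital-sign, EKG and laboratory summaries, and the rescue-censored visual acuity summaries, still cover the follow-up visits.

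**What to change.** Amend SAP 4.3.1 so that AEs with onset from the first Lucentis injection through Study Exit are tabulated. Either of two wordings would do:

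- extend the treatment-emergent definition to Study Exit; or
- keep that term for on-treatment events and lift the restriction for the Follow-up and entire-study tables.

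In both cases, assign each AE to a period by its onset date under Table 2. Add a rule to Table 2 for subjects with no Week 24 visit. One example is to end On-treatment on Day 169 and start Follow-up on Day 170. The rule should also say whether a visit elsewhere in the Day 156 to 183 analysis window counts as the Week 24 visit for this purpose. A flag for AEs starting after a rescue injection is optional.

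The cost is one sentence and one boundary rule. AEs are already collected to study exit, so no new data are needed. The small downside is that the Follow-up tables will include some events that occur after rescue anti-VEGF treatment.
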